In this trial, patients will receive a fixed dose of 1500mg IV infusion every four weeks with concurrent chemotherapy and then every 4 weeks in the consolidative phase. Although the PACIFIC trial administered durvalumab every 2 weeks for up to one year, monthly administration improves convenience, has been shown not to compromise safety or efficacy and is the dosing regimen employed in the PACIFIC2 trial. A population PK model was developed for durvalumab using monotherapy data from a Phase I study (study 1108; N=292; doses= 0.1 to 10 mg/kg Q2W or 15 mg/kg Q3W; solid tumors). Population PK analysis indicated only minor impact of body weight (WT)

# UTSouthwestern Harold C.Simmons Comprehensive Cancer Center

on the PK of durvalumab (coefficient of ≤0.5). The impact of body WT-based (10 mg/kg Q2W) and fixed dosing (750 mg Q2W) of durvalumab was evaluated by comparing predicted steady state PK concentrations (5th, median and 95th percentiles) using the population PK model. A fixed dose of 750 mg was selected to approximate 10 mg/kg (based on median body WT of ~75 kg). A total of 1,000 patients were simulated using body WT distribution of 40–120 kg. Simulation results demonstrate that body WT-based and fixed dosing regimens yield similar median steady state PK concentrations with slightly less overall between-patient variability with fixed dosing regimen.

Similar findings have been reported by others (Ng et al 2006, Wang et al 2009, Zhang et al 2012, Narwal et al 2013). Wang and colleagues investigated 12 monoclonal antibodies and found that fixed and body size-based dosing perform similarly, with fixed dosing being better for 7 of 12 antibodies (Wang et al 2009)]. In addition, they investigated 18 therapeutic proteins and peptides and showed that fixed dosing performed better for 12 of 18 in terms of reducing the between-patient variability in pharmacokinetic/pharmacodynamics parameters (Zhang et al 2012).

A fixed dosing approach is preferred by the prescribing community due to ease of use and reduced dosing errors. Given expectation of similar pharmacokinetic exposure and variability, we considered it feasible to switch to fixed dosing regimens. Based on average body WT of 75 kg, a fixed dose of 1500 mg Q4W durvalumab (equivalent to 20 mg/kg Q4W) is included in the current study.

#### 1.5 Correlative Studies

# 1.5.1 Tumor PD-L1 Expression

The effect of tumor PD-L1 expression on treatment response to anti-PD-L1 targeted immunotherapy is a key focus of ongoing investigation. Identification of predictive biomarkers of response to therapy protects patients from exposure to risks of ineffective therapies and improves cost-effectiveness. Submission of formalin-fixed and paraffin embedded tumor samples (blocks) from core or excisional biopsy is recommended for all patients at the time of study enrollment. Although PD-L1 expression has been associated with improved outcomes from anti-PD1/PD-L1 therapy in advanced NSCLC, the benefit has been less apparent in trials combining these agents with other therapies, including cytotoxic chemotherapy for stage 4 disease (Herbst et al., 2016; Langer et al., 2016; Socinski et al., 2018) or chemoradiation (Antonia et al., 2018). Based on the results of KEYNOTE-021 cohort G, a randomized phase II trial, the U.S. Food and Drug Administration has approved the triple combination of carboplatin, pemetrexed, and pembrolizumab in all patients with non-squamous cell NSCLC, regardless of PD-L1 expression levels (Langer et al., 2016). Previously reported results from the IMpower150 study showed that the combination of TECENTRIQ and Avastin plus carboplatin and paclitaxel has longer progression-free survival compared to Avastin plus carboplatin and paclitaxel in the first-line treatment of people with advanced non-squamous NSCLC (Socinski et al., 2018). This PFS benefit was observed across key subgroups, including those with varying levels of PD-L1 expression. Finally, as noted above, PDL1 levels may change after administration of radiation therapy. We therefore hypothesize that any association between tumor PD-L1 expression and clinical outcomes will be modest in this trial. Analysis of PD-L1 expression and other biomarkers may be evaluated as determined by additional data associated with disease progression or response to durvalumab.

#### 1.5.2 Optional tumor tissue collection and studies

If a standard-of-care diagnostic biopsy to confirm recurrence is obtained, at least two core biopsies, minimum, should be obtained as part of this recurrence biopsy. Paraffin embedded tissue from this biopsy will be used for confirmation of recurrence and for additional research. Any remaining tumor tissue will be stored for additional research. Patients may consent to have tissue and/or blood submitted at recurrence.

The remaining tumor samples may be used to analyze the expression and spatial distribution of immune-related or response-related markers by multiplex immunohistochemistry, which may include but are not limited to PD-L1, CTLA-4, CD3, CD4, CD8, CD45RO, FOXP3, granzyme B,

OX40, PD1, cleaved caspase 3, and Ki67. Archived material (or biopsies if available) may also be analyzed for the presence of key genomic features such as *EGFR*, *KRAS*, and *ALK* alterations to evaluate their potential relevance and correlations with response to durvalumab.

#### 1.5.3 Optional blood collection for blood born biomarkers

Blood samples will be analyzed to evaluate protein, nucleic acid, and cellular biomarkers that relate to durvalumab. PBMC will also be isolated from whole blood and will be preserved, and may be used for subsequent flow cytometry or assessment of the diversity of the immune cell repertoire based on VDJ coding region analysis, the relationship to clinical responses, and changes in response to treatment with durvalumab. Blood collected for analysis of immune cell gene expression profiles within the peripheral compartments will be evaluated for any relationship with efficacy endpoints. Serum samples may also be anlayzed for analysis of circulating soluble factors in relation to immune status at baseline and in response to treatment. Factors to be analyzed may include but are not limited to IFN-γ, tumour necrosis factor-α, interleukin (IL)-2, IL-6, IL-10, IL-8, IL-12, and levels of soluble PD-L1.

Recent studies have found that more than 25% of healthy individuals have strong IgG humoral immune responses to a variety of self-antigens, indicating that a "benign" form autoimmunity is much more common than autoimmune disease (Wandstrat et al., 2006). This autoimmunity is directed against a variety of self-antigens. These findings indicate that many healthy individuals exhibit significant autoimmunity that is regulated in the peripheral immune system by pathways such as those triggered by CTLA-4 and PD1. Consistent with this, CTLA-4 and PD1 are both known to potentiate autoimmune disease, suggesting that the inhibition of these regulatory pathways aggravates pre-existing autoimmunity. Based on this, we hypothesize that checkpoint therapy immune-related adverse events often result from the activation of pre-existing autoimmunity.

We have the capacity to this hypothesis by utilizing a variety of novel technologies to quantify autoimmune responses. Specifically, we have the ability to measure IgG autoantibody reactivity against more than 120 systemic and organ-specific antigens simultaneously.

The protein array system that we have developed for autoantibody screening can also be used to assess antibodies against any antigen. Consequently, a panel of tumor-type-specific antigens may be incorporated into these arrays so that we can follow the level and specificity of anti-tumor humoral immunity elicited by checkpoint therapy in individual patients and correlate this with disease progression.

# 2.0 STUDY OBJECTIVES

# 2.1 Primary Objectives

2.1.1 To determine the 12-month progression-free survival (PFS) rate for Stage III non-small lung cancer patients treated with concurrent durvalumab and radiotherapy followed by consolidative durvalumab;

# 2.2 Secondary Objectives

- 2.2.1 To assess the safety and tolerability of concurrent durvalumab and radiotherapy compared to historical data from patients treated with standard of care chemoradiation;
- 2.2.2 To determine the overall survival (OS) defined as the time from study enrollment to death due to any cause;
- 2.2.3 To determine the distant metastases-free survival defined as the time from the study enrollment to any new distant lesion;
- 2.2.4 To determine the local and regional control defined as the time from the study enrollment to any local and regional lesion;

# 2.3 Exploratory Objectives

- 2.3.1 Biomarker and biomarker correlatives: To determine the OS and PFS in patients with (1) PD-L1-positive, (2) PD-L1-negative tumors and (3) PD-L1 not evaluable/undetermined tumors.
- 2.3.2 Proportion of patients alive at 12 and 24 months;

### 2.4 Endpoints

- 2.4.1 Primary endpoint of 12-month progression-free survival (PFS) rate is based on an assessment by an investigators according to RECIST 1.1 criteria; PFS is defined as the time from the study enrollment to documented progressive disease or death due to any cause, whichever occurs first;
- 2.4.2 Secondary endpoint of safety and tolerability will be assessed by adverse event according to CTCAE V.5;
- 2.4.3 Secondary endpoint of overall survival is defined as the time from study enrollment to death due to any cause;
- 2.4.4 Secondary endpoint of distant metastases free survival is defined as the time from the study enrollment to any new distant lesion;
- 2.4.5 Secondary endpoint of local and regional control defined as the time from the study enrollment to any local and regional lesion;
- 2.4.6 Exploratory endpoint of biomarker and biomarker correlatives;
- 2.4.7 Exploratory endpoint of proportion of patients alive at 12 and 24 months.

# 3.0 Subject ELIGIBILITY

Eligibility waivers are not permitted. Subjects must meet all of the inclusion and exclusion criteria to be registered to the study. Study treatment may not begin until a subject is registered.

#### 3.1 Inclusion Criteria

- 3.1.1 Pathologically (histologically or cytologically) proven diagnosis of NSCLC with, medically inoperable (or patients who refuse resection) stage IIIA or stage IIIB disease (AJCC 8th edition);
  - 3.1.1.1 Inoperable Stage IIIA disease is defined by multiple and/or bulky N2 mediastinal lymph nodes on computed tomography (CT) scan such that, in the opinion of the treating investigator, the patient was not a candidate for surgical resection.
  - 3.1.1.2 N2 disease must have been documented by biopsy, or at a minimum by fluorodeoxyglucose positron emission tomography (PET) or CT if nodes were more than 2 cm in short axis diameter.
  - 3.1.1.3 T4 disease is often considered resectable at the discretion of a thoracic surgeon. Patients with T4N0 or T4N1 disease can be enrolled if their case is reviewed by a thoracic surgeon and felt to be unresectable or if they are either medically inoperable or refuse surgery.
  - 3.1.1.4 Stage IIIB patients have N3 or T4N2 status. N3 status must have been documented by the presence of a contralateral (to the primary tumor) mediastinal lymph node or supraclavicular or scalene lymph node proven by biopsy, or at a minimum by fluorodeoxyglucose uptake on PET or more than 2 cm in short axis diameter on CT scan. Patients with disease extending into the cervical region (defined as disease extending above cricoid cartilage) are not eligible.
- 3.1.2 Appropriate stage for study entry based on the following diagnostic workup:
  - 3.1.2.1 History/physical examination, including documentation of height, weight and vital signs, within 30 days prior to registration;
  - 3.1.2.2 CT scan with IV contrast (CT scan without contrast acceptable if IV contrast is medically contraindicated) of the lung and upper abdomen through the adrenal glands within 60 days prior to registration (recommended within 30 days prior to registration);

# UTSouthwestern Harold C.Simmons Comprehensive Cancer Center

- 3.1.2.3 MRI of the brain with contrast (or CT with contrast if MRI is medically contraindicated) within 60 days prior to registration; note: the use of intravenous contrast is required for the MRI or CT (unless medically contra-indicated).
- 3.1.2.4 Whole-body FDG-PET/CT within 60 days prior to registration;
- 3.1.3 Age ≥ 18 years;
- 3.1.4 Life expectancy ≥ 12 weeks
- 3.1.5 Zubrod Performance Status of 0-1 within 30 days prior to registration;
- 3.1.6 Adequate respiratory function within 180 days prior to registration defined as follows: FEV1 > 1.2 liters; DLCO ≥ 50% predicted;
- 3.1.7 Patients with post-obstructive pneumonia are eligible provided they no longer require intravenous antibiotics at registration;
- 3.1.8 Patients with a pleural effusion that is transudative, cytologically negative and non-bloody, are eligible if the radiation oncologist feels the tumor can be encompassed within a reasonable field of radiotherapy; if pleural fluid is too small a volume to effectively sample by thoracentesis and does not show increased metabolic activity on CT/PET imaging, the patient will be remain eligible.
- 3.1.9 Adequate organ and marrow function as defined below
  - 3.1.9.1 Absolute neutrophil count >1.5 × 10^9/L
  - 3.1.9.2 Platelet count >100 × 109/L
  - 3.1.9.3 Baseline or post-transfusion Hemoglobin ≥9.0 g/dL
  - 3.1.9.4 Serum bilirubin≤ 1.5x upper limit of normal (ULN). This will not apply to patients with confirmed Gilbert's syndrome, who will be allowed in consultation with their physician.
  - 3.1.9.5 Alanine aminotransferase (ALT) and aspartate aminotransferase (AST) ≤ 2.5x ULN.
  - 3.1.9.6 Measured creatinine clearance (CL) >40 mL/min or calculated CL >40 mL/min as determined by Cockcroft-Gault (using actual body weight);

#### Males:

Creatinine CL = Weight (kg) × (140 - Age) (mL/min) 72 × serum creatinine (mg/dL)

# Females:

Creatinine CL = Weight (kg) × (140 - Age) × 0.85 (mL/min) 72 × serum creatinine (mg/dL)

- 3.1.10 Negative serum pregnancy test within three days prior to registration for women of childbearing potential.
- 3.1.11 Women of child-bearing potential and men must agree to use adequate contraception (hormonal or barrier method of birth control; abstinence) prior to study entry, for the duration of study participation, and for 90 days following completion of therapy. Should a woman become pregnant or suspect she is pregnant while participating in this study, she should inform her treating physician immediately.
  - 3.1.12.1 A female of child-bearing potential is any woman (regardless of sexual orientation, having undergone a tubal ligation, or remaining celibate by choice) who meets the following criteria:
    - Has not undergone a hysterectomy or bilateral oophorectomy; or
    - Has not been naturally postmenopausal for at least 12 consecutive months (i.e., has had menses at any time in the preceding 12 consecutive months).
  - 3.1.12.2 Evidence of post-menopausal status or negative urinary or serum pregnancy test for female pre-menopausal patients. Women will be considered post-menopausal if they have been amenorrheic for 12 months

without an alternative medical cause. The following age-specific requirements apply:

- Women <50 years of age would be considered post-menopausal if they
  have been amenorrheic for 12 months or more following cessation of
  exogenous hormonal treatments and if they have luteinizing hormone
  and follicle-stimulating hormone levels in the post-menopausal range for
  the institution or underwent surgical sterilization (bilateral oophorectomy
  or hysterectomy).

- Women ≥50 years of age would be considered post-menopausal if they
  have been amenorrheic for 12 months or more following cessation of all
  exogenous hormonal treatments, had radiation-induced menopause with
  last menses >1 year ago, had chemotherapy-induced menopause with
  last menses >1 year ago, or underwent surgical sterilization (bilateral
  oophorectomy, bilateral salpingectomy or hysterectomy).
- 3.1.12 Ability to understand and the willingness to sign a written informed consent.

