**Table 1. Safety Summary of Pacific Trial** 

Event	Durvalumat	(N=475)	Placebo	(N = 234)
	Any Grade*	Grade 3 or 4	Any Grade*	Grade 3 or 4
	nur	nber of patients with e	event (percent)	
Any event	460 (96.8)	142 (29.9)	222 (94.9)	61 (26.1)
Cough	168 (35.4)	2 (0.4)	59 (25.2)	1 (0.4)
Pneumonitis or radiation pneumonitis†	161 (33.9)	16 (3.4)	58 (24.8)	6 (2.6)
Fatigue	113 (23.8)	1 (0.2)	48 (20.5)	3 (1.3)
Dyspnea	106 (22.3)	7 (1.5)	56 (23.9)	6 (2.6)
Diarrhea	87 (18.3)	3 (0.6)	44 (18.8)	3 (1.3)
Pyrexia	70 (14.7)	1 (0.2)	21 (9.0)	0
Decreased appetite	68 (14.3)	1 (0.2)	30 (12.8)	2 (0.9)
Nausea	66 (13.9)	0	31 (13.2)	0
Pneumonia	62 (13.1)	21 (4.4)	18 (7.7)	9 (3.8)
Arthralgia	59 (12.4)	0	26 (11.1)	0
Pruritus	58 (12.2)	0	11 (4.7)	0
Rash	58 (12.2)	1 (0.2)	17 (7.3)	0
Upper respiratory tract infection	58 (12.2)	1 (0.2)	23 (9.8)	0
Constipation	56 (11.8)	1 (0.2)	20 (8.5)	0
Hypothyroidism	55 (11.6)	1 (0.2)	4 (1.7)	0
Headache	52 (10.9)	1 (0.2)	21 (9.0)	2 (0.9)
Asthenia	51 (10.7)	3 (0.6)	31 (13.2)	1 (0.4)
Back pain	50 (10.5)	1 (0.2)	27 (11.5)	1 (0.4)
Musculoskeletal pain	39 (8.2)	3 (0.6)	24 (10.3)	1 (0.4)
Anemia	36 (7.6)	14 (2.9)	25 (10.7)	8 (3.4)

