# TABLE 2: FREE BREATHING / ABDOMINAL COMPRESSION / ACTIVE BREATH HOLD / GATING MOTION MANAGEMENT TECHNIQUES

DICOM Standard Name	Description	Detailed Specification			
GTV_6000	GTV to receive 60 Gy  Required for free breathing, active breath hold or gating motion management techniques	,			
CTV_6000	CTV to receive 60 Gy  Required	The CTV is defined to be the GTV plus a 0.5 cm margin to account for microscopic tumor extension. If an ITV is used, then a 0.5 cm margin is added to the ITV to form a CTV. The CTV should be adjusted to not expand into other organs such as esophagus, major blood vessels, or bone.			
PTV_6000	PTV to receive 60 Gy  Required	The PTV will be equal to the CTV+IM+SM. IM and SM are defined in Section 5.2.4 above. In cases in which the PTV expansion extends outside of the skin, towards the spinal cord or into the spinal canal, it can be assumed that tumor motion will not occur in this direction, and the PTV margin in this direction can be limited. PTV margin can be limited up to 0.5 cm towards this particular dimension (skin or spinal cord).			

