#### 5.6 Study Restrictions

#### Female patient of child-bearing potential

Female patients of childbearing potential who are not abstinent and intend to be sexually active with a non-sterilized male partner must use at least 1 highly effective method of contraception from the time of screening throughout the total duration of the drug treatment and the drug washout period (90 days after the last dose of durvalumab monotherapy). Non-sterilized male partners of a female patient of childbearing potential must use male condom plus spermicide throughout this period. Cessation of birth control after this point should be discussed with a responsible physician. Periodic abstinence, the rhythm method, and the withdrawal method are not acceptable methods of birth control. Female patients should also refrain from breastfeeding throughout this period.

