#### Male patients with a female partner of childbearing potential

Non-sterilized male patients who are not abstinent and intend to be sexually active with a female partner of childbearing potential must use a male condom plus spermicide from the time of screening throughout the total duration of the drug treatment and the drug washout period (90 days after the last dose of durvalumab monotherapy). However, periodic abstinence, the rhythm method, and the withdrawal method are not acceptable methods of contraception. Male patients should refrain from sperm donation throughout this period.

Female partners (of childbearing potential) of male patients must also use a highly effective method of contraception throughout this period.

Females of childbearing potential are defined as those who are not surgically sterile (ie, bilateral salpingectomy, bilateral oophorectomy, or complete hysterectomy) or post-menopausal.

Women will be considered post-menopausal if they have been amenorrheic for 12 months without an alternative medical cause. The following age-specific requirements apply:

- Women <50 years of age would be considered post-menopausal if they have been amenorrheic for 12 months or more following cessation of exogenous hormonal treatments and if they have luteinizing hormone and follicle-stimulating hormone levels in the post-menopausal range for the institution.
- Women ≥50 years of age would be considered post-menopausal if they have been amenorrheic for 12 months or more following cessation of all exogenous hormonal treatments, had radiation-induced menopause with last menses >1 year ago, had chemotherapy-induced menopause with last menses >1 year ago.

Highly effective methods of contraception, defined as one that results in a low failure rate (ie, less than 1% per year) when used consistently and correctly are described in Table 2. Note that some contraception methods are not considered highly effective (e.g. male or female condom with or without spermicide; female cap, diaphragm, or sponge with or without spermicide; non-copper containing intrauterine device; progestogen-only oral hormonal contraceptive pills where inhibition of ovulation is not the primary mode of action [excluding Cerazette/desogestrel which is considered highly effective]; and triphasic combined oral contraceptive pills).

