#### **Table 1. Highly Effective Methods of Contraception (<1% Failure Rate)**

Barrier/Intrauterine methods	
 
Hormonal Methods
 

Copper T intrauterine device     Levonorgestrel-releasing intrauterine system (e.g., Mirena®) a	
 
Hormonal Methods
 
Implants: Etonogestrel-releasing implants: e.g. Implanon® or Norplant®
 
Intravaginal:         Ethinylestradiol/etonogestrel-releasing intravaginal devices: e.g. NuvaRing®
 
Injection: Medroxyprogesterone injection: e.g. Depo-Provera®
 
Combined Pill: Normal and low dose combined oral contraceptive pill
 
Patch:         Norelgestromin/ethinylestradiol-releasing transdermal system: e.g.         Ortho Evra®
 
Minipillc: Progesterone based oral contraceptive pill using desogestrel: Cerazette® is currently the only highly effective progesterone-based
 

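### Section 3.1.11 accepts weaker contraception than 5.6 requires of women and men, and the only timed pre-treatment pregnancy test is tied to registration, with none listed during concurrent treatment

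*Combined protocol and SAP*

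**What the plan says.** Inclusion criterion 3.1.11 applies to men and to women of childbearing potential. It explains adequate contraception as "hormonal or barrier method of birth control; abstinence". It runs through study participation and for 90 days after therapy ends.

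Section 5.6 sets a different standard. Women who are sexually active with an unsterilised male partner "must use at least 1 highly effective method of contraception from the time of screening". Methods named there as not highly effective include "male or female condom with or without spermicide; female cap, diaphragm, or sponge with or without spermicide". Unsterilised men with a partner of childbearing potential "must use a male condom plus spermicide from the time of screening", and the partner must also use a highly effective method. For both sexes the obligation ends 90 days after the last durvalumab dose. The section says the acceptable methods, "when used consistently and correctly are described in Table 2", but Table 2 is the radiotherapy motion-management table. The contraception list is headed Table 1.

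On testing, 3.1.10 and the pre-treatment table in 5.4 ask for a negative serum test within 3 days before registration. Section 3.1.12.2 mentions a urine or serum test without a window, and the 90-day screening default in 5.1 also counts back from registration. Neither 5.2.1 nor the concurrent-phase table in 5.4 lists a pregnancy test. The consolidation table does, every 6 weeks.

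**The concern.** Exclusion criterion 3.2.9 justifies its contraception rule by saying the treatment could seriously harm a fetus. The safeguards should therefore be tightest when exposure begins.

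As written, a coordinator who applies the eligibility criteria correctly can register a patient who is already out of line with 5.6. Sections 3.0 and 11.3 tie registration to the criteria, and neither points to 5.6.

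Treatment can then begin on a pregnancy test that was fresh at registration but not at first exposure, and a second infusion can follow without another test. The other protections are the woman's own report of a suspected pregnancy (3.1.11) and stopping the drug (7.3.2). Both act only once pregnancy is suspected or known.

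**Working it through.** **Contraception, side by side** (the 5.6 column applies to patients who are not abstinent)

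| | 3.1.11 and 3.1.12.1 | 5.6 |
|---|---|---|
| Women | Any one of hormonal, barrier, abstinence | At least one highly effective method; condom, cap, diaphragm and sponge do not qualify; the unsterilised partner adds condom with spermicide |
| Men | Same list, so a condom alone is enough | Condom with spermicide, plus a highly effective method for the partner |
| End | Study participation, and 90 days after therapy | 90 days after last durvalumab |
| Surgery that ends childbearing potential | Hysterectomy or bilateral oophorectomy | Also bilateral salpingectomy |

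The entry standard is lower for both sexes. The end dates also differ: follow-up under 4.6 lasts for years, so study participation can run far beyond 90 days after the last dose. Replacing only the parenthesis in 3.1.11 would attach the stricter method to that longer period.

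**Age of the pregnancy test**

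The plan states no figure of its own to reproduce. Inputs:

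- Test to registration: at most 3 days (3.1.10; 5.4).
- Registration to radiotherapy start, S: 14 days for Per Protocol, 15 to 30 for Variation Acceptable (4.4.8, delivery criteria). This takes the 14 as an upper limit and step 1 registration as the study registration, the only one that 11.3 describes.
- First durvalumab: within 3 days either side of radiotherapy start (4.1.1).
- Second durvalumab: 28 ± 3 days after the first (4.1.1).

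Largest age at radiotherapy start = 3 + S. Add 3 for first durvalumab, and 28 + 3 = 31 more for the second.

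| Event | Per Protocol | Variation Acceptable |
|---|---|---|
| Radiotherapy start | 3 + 14 = 17 days | 3 + 30 = 33 days |
| First durvalumab | 17 + 3 = 20 days | 33 + 3 = 36 days |
| Second durvalumab | 20 + 31 = 51 days | 36 + 31 = 67 days |

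**Does the second infusion fall in the concurrent phase?** Relative to radiotherapy start, it comes between −3 + 25 = 22 and 3 + 31 = 34 days later, so at the latest on calendar day 35. Thirty weekday fractions without interruption end on calendar day 40 (Monday start) or 42 (any other weekday). It therefore falls before the last fraction, in the phase with no listed test.

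**With a test within 3 days before first study treatment:** at most 3 days old at that treatment, and at most 3 + 3 = 6 days old when the other component starts.

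**The case against.** The strongest reply is that nothing conflicts in practice: 5.6 already applies from screening, and a patient who follows it meets both rules. In addition, 3.2.9 excludes anyone who will not or cannot use contraception that is medically acceptable. This stands as far as it goes. A reader might infer that the protocol permits barrier-only contraception during treatment; it does not, because 5.6 forbids it for the patients it covers. What remains is that the 3.2.9 standard is undefined and the registration check does not cite 5.6.

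Section 3.1.11 might also be shorthand for the contraception list, whose columns are headed barrier/intrauterine and hormonal. But 5.6 expressly rules out the ordinary barrier methods, so the shorthand would mislead.

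On size, 5.6 defines highly effective as a failure rate below 1% per year. Over 67 days that gives less than 1% × 67/365 = 0.18% per woman, or fewer than 5 × 0.0018 = 0.009 expected pregnancies if five women are affected (an assumed number). This is a fair argument that the risk is small. It presumes, however, that every woman is using a 5.6 method, which the entry criterion does not secure. The documents give no failure rate for barrier methods, so no figure can be put on the other case.

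The test ages are maxima within scoring categories. A reader might take 17 and 33 days as typical, or as caps. They are neither: an earlier start gives a fresher test, and a start after day 30 is scored as Deviation Unacceptable but not prohibited. In the copy reviewed, the right-hand column of the pre-treatment table is cut off, so an entry there cannot be fully excluded. If the sponsor's copy has a pregnancy test in that column, the second item of the fix may be unnecessary.

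Two further inferences are not supported. The wrong table number does not leave staff without a list, since the correctly titled table directly follows the text; it is clerical. And 6-weekly testing in consolidation, under a monthly column heading, is a choice of frequency that nothing in the documents shows to be inadequate.

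**Conclusion.** The point holds as a safety and consistency defect. The eligibility wording is weaker than 5.6 for women and for men, and the registration check rests on the weaker wording. The only timed pre-treatment test can be up to 17 or 33 days old at radiotherapy start and up to 20 or 36 days old at first durvalumab, depending on the scoring category. No test is listed between registration and consolidation.

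The day counts rest on reading step 1 registration as study registration and on inclusive window limits. The number of women of childbearing potential is not stated and is likely to be small; 0 to 5 of the 50 patients is an assumption. Progression-free survival, sample size and error rates are unaffected. The case for acting is that the possible harm is serious and avoidable and the remedy is cheap, not that the event is likely.

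**What to change.** 1. Reword 3.1.11 for both sexes so that patients agree to use contraception as Section 5.6 requires, from screening until 90 days after the last durvalumab dose. This replaces both the parenthesis and the separate duration. Use one definition of childbearing potential in 3.1.12.1 and 5.6, stating whether bilateral salpingectomy counts as sterile. As a clerical item, correct the Table 2 pointer in 5.6, citing the contraception table by title because the PACIFIC safety table is also numbered Table 1.
2. Keep 3.1.10. Add a negative serum or urine pregnancy test within 3 days before first study treatment (radiotherapy or durvalumab, whichever comes first), needed only if the registration test is older than that.
3. Add a serum or urine test at the existing week 5 durvalumab visit, in 5.2.1 and in the concurrent-phase table, with the result available before the infusion.

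Cost: amendment wording and at most two added tests per affected woman. For an assumed 0 to 5 women, that is 2 × 0 = 0 to 2 × 5 = 10 tests in the whole trial. The week 5 test uses an existing visit, and the pre-treatment test can be done on the first treatment day. The consolidation schedule stays as it is.
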